## Tear Lipid Layer Thickness with Emollient Eye Drops

This study will objectively evaluate two FDA approved artificial tear formulations (Allergan, plc) Refresh Optive and Refresh Optive MEGA-3 in subjects with dry eye symptoms and lipid layer thickness - LLT< 65 nm at baseline in a randomized, cross-over (masked subject) design. We seek to objectively evaluate the increase in lipid layer thickness from baseline at 15 minutes and 1, 2 and 4 hours after an eye drop has been instilled.

Korb, et al (Optom Vis Sci, 2005) have previously shown that an emollient eye drop, will increase the lipid layer of the tear film from ~ 75 to 125nm. We successfully confirmed this with our own IRB approved study at OSU in 2015-2016 which has been accepted for publication. In that previous study, using an emollient eye drop a non-emollient eye drop and our interferometric system, we had no adverse events. The eye drops used in this study will be over-the-counter emollient and non-emollient eye drops made by a different manufacturer than the previous studies.

### Objective

To measure and compare the increase in lipid layer thickness of the tear film and symptoms in dry eye patients with a deficient lipid layer 15 minutes and 1 hour after the instillation of an emollient eye drop or a non-emollient eye drop. This is a pilot study to help determine sample size in future studies.

### Study Overview

This 20 subject pilot, crossover study will test the lipid layer thickness and morphology of two dry eye related products. All subjects will test one product and following a minimum of a 2-day washout, the same subjects will test another product.

The subjects will have a baseline examination and baseline lipid layer imaging using the King-Smith Stroboscopic Video Color Microscope (SVCM). The baseline examination should last 1 ½ hours. If all criteria are met to continue the study, the 1st eye drop exposure visit will be scheduled or may begin immediately as time allows.

For each eye drop exposure and measurement visit, the eye drop will be applied as to not stimulate tearing or nor apply pressure that would express meibum, and then measurements with the SVCM will be made at 15 minutes, and 1 hour. This will be accomplished at one visit lasting 2 hours. Subjects are permitted to leave and return between the 15 minute and later measurement- but will be instructed not to use any eye drops, eye makeup and not to touch or rub their eyes during that time.

It is anticipated that up to 50 subjects may need to be screened to obtain the 20 to 30 subjects to enter into the study to complete 20 subjects.

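### Each product's rise in lipid layer thickness is measured from the same low reading that selects subjects, so it includes regression to the mean

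*Protocol*

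**What the plan says.** The opening section (Tear Lipid Layer Thickness with Emollient Eye Drops) states the aim: "We seek to objectively evaluate the increase in lipid layer thickness from baseline". The Objective repeats it: "To measure and compare the increase in lipid layer thickness of the tear film". Each product's own rise is therefore an aim, alongside the comparison of the two.

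The Study Overview describes one baseline session: "The subjects will have a baseline examination and baseline lipid layer imaging", using the SVCM. That session leads to entry. The next step is conditional, "If all criteria are met to continue the study", and the first "eye drop exposure visit will be scheduled or may begin immediately as time allows". Low LLT is one of the criteria. The opening section requires "lipid layer thickness - LLT< 65 nm at baseline", and the Inclusion criteria set a limit of 75 nm on the SVCM. The two limits differ and need reconciling, but the present point arises under either.

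At each exposure visit the order is drop first, "and then measurements with the SVCM will be made at 15 minutes, and 1 hour". Neither exposure visit lists a reading before the drop. The second product is tested at least 2 days after the first.

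**The concern.** The selecting variable, the reference value and the outcome are the same quantity on the same instrument, and the first two come from the same session. A subject can fall below the LLT limit because the lipid layer is usually thin or because it happened to read low that day. The second component does not persist, so the group mean rises at later readings without any treatment. Measured from the selecting session, that rise is credited to the product.

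A drop with no effect could then appear to thicken the lipid layer, and an effective drop would look somewhat better than it is. In relative terms the distortion is greatest for whichever product has the smaller true effect. Without a pre-drop reading in period 2, there is also no way to check that LLT has returned to its starting level after the washout.

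**Working it through.** The protocol has no power calculation, SD or repeatability figure, so there is no stated figure to reproduce. What follows sizes the bias.

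**Inputs from the protocol**
- Selected fraction *p*: the Study Overview says "up to 50 subjects may need to be screened to obtain the 20 to 30 subjects", which gives 20/50 = 0.4 to 30/50 = 0.6. This is a proxy, because it treats every screen failure as an LLT failure.
- Reference effect: the opening section cites a rise from about 75 to 125 nm, that is 50 nm.

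**Assumed inputs**
- SD of LLT among candidates: 15 to 30 nm.
- Correlation *r* between readings on different days: 0.5 to 0.9.
- Alternative selected fraction of 0.8, for the case where other criteria cause many of the screen failures.

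**Formula.** For a normally distributed baseline cut at its *p*-th quantile, with no product effect:

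spurious increase = (1 − r) × SD × φ(z)/p, where z = Φ⁻¹(p)

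φ(z)/p is 0.966, 0.798, 0.644 and 0.350 at p = 0.4, 0.5, 0.6 and 0.8.

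| Case | p | SD (nm) | r | Spurious increase (nm) | Share of 50 nm |
|---|---|---|---|---|---|
| Lowest, p 0.4–0.6 | 0.6 | 15 | 0.9 | 0.1 × 15 × 0.644 = 0.97 | 2% |
| Middle | 0.5 | 20 | 0.7 | 0.3 × 20 × 0.798 = 4.79 | 10% |
| Highest, p 0.4–0.6 | 0.4 | 30 | 0.5 | 0.5 × 30 × 0.966 = 14.49 | 29% |
| p = 0.8, lowest | 0.8 | 15 | 0.9 | 0.1 × 15 × 0.350 = 0.52 | 1% |
| p = 0.8, highest | 0.8 | 30 | 0.5 | 0.5 × 30 × 0.350 = 5.25 | about 11% |

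**Simulation.** With both products set to no effect, the mean change from the selecting baseline was 4.78 and 4.79 nm for the two products in the middle case, 14.48 and 14.46 nm in the highest, and 0.96 nm for both in the lowest. The difference between products stayed within 0.02 nm of zero. Measured from a fresh pre-drop reading, the change was between −0.02 and 0.00 nm. In a separate middle-case simulation, a true between-product difference of 50 nm was recovered as 50.0 nm.

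**Same-day start.** If period 1 follows the baseline session at once, the day-to-day part of the within-subject variation is shared and only the within-day part regresses. The middle-case bias in period 1 becomes 4.79 × (1 − day share), which is 3.6, 2.4 or 1.2 nm when day variation is 25%, 50% or 75% of within-subject variance. Period 2 keeps the full 4.8 nm.

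**Precision of the between-product comparison (middle case).** Within-subject variance is 0.3 × 20² = 120. The paired post-drop difference has SD √(2 × 120) = 15.5 nm. Subtracting one pre-drop reading per visit gives √(4 × 120 × (1 − day share)) = 19.0, 15.5 or 11.0 nm at the same three day shares. Subtraction can therefore help or hurt, depending on repeatability within a visit.

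**Illustration only, since the protocol names no test.** With 20 subjects, a paired t test against the selecting baseline at the two-sided 5% level would show a false increase in about 28% of null trials in the middle case, and about 9% to 61% over p 0.4–0.6 and r 0.5–0.9. The nominal rate is 2.5%.

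**The case against.** The strongest reply is that the protocol is silent rather than wrong. It does not say which reading is subtracted, it does not exclude a pre-drop reading, and each 2-hour visit has time for one. The definition of baseline is often left to the analysis plan. This stands in part: the bias is what follows if a site does exactly what is written. But when the instrument is used is a visit procedure fixed in the protocol, and no analysis plan can recover a reading that was never taken.

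A second reply is that the screening and baseline sessions may differ, since the Inclusion criteria and the Study Overview give different durations, or that several images may be averaged. Averaging would shrink the measurement-error part of the bias. However, the opening section ties the LLT limit to baseline, and the Study Overview describes no other baseline imaging.

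Third, the randomised crossover protects the main contrast, and the study is a pilot for sizing later work. That is correct. The paired difference is unbiased, and so are the inputs for planning a paired comparison. The bias is confined to each product's own increase, which is still a stated aim. A pre-drop reading would remove the selection bias but not time-of-day or instillation effects, so even the corrected increase is not a pure product effect.

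Finally, the size rests on assumed values, and the Exclusion criteria give many other reasons for screen failure. That also stands, and is why the 80% case is shown. The upward direction does not depend on those values, short of perfect agreement between readings.

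**Conclusion.** The concern holds. As written, each product's increase is measured from the session that selected subjects for low LLT, and it is biased upward by regression to the mean. The size is about 1 to 14.5 nm per product if 40–60% of candidates are selected on LLT, and 0.5 to 5.3 nm if 80% are. The middle value of 4.8 nm is about a tenth of the rise the protocol cites. These figures rest on a normal distribution and on an SD and correlation that the protocol does not give, so the direction is firm and the size is only indicative. The comparison between products is unaffected. The point should be corrected, but it does not undermine the trial's main contrast.

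**What to change.** In the Study Overview, add an SVCM reading immediately before the drop at each exposure visit, separate from the reading used for eligibility even when period 1 starts on the same day. Define each product's increase as the change from that visit's pre-drop value, and use the period-2 pre-drop reading to check return to baseline after the washout. Keep the paired post-drop difference as the between-product comparison unless within-visit repeatability shows that subtracting the pre-drop value improves precision.

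The cost is two short recordings per subject, on the same instrument, with the same staff and within the existing visits. If a pre-drop reading is already intended, one sentence saying so is enough.

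If no reading is added, state that conclusions are limited to the paired between-product difference and that increases from the screening image will not be interpreted as product effects. That costs one sentence, but gives up each product's own increase as an aim.

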## Eligibility and Exclusion Criteria

### Inclusion criteria:

- Age – at least 30 years
- Good general health (defined by medication use that has not changed within the last month and the absence of medical conditions or treatments that are deemed confounding to the data as determined by the PI)
- Ability to give informed consent
- Willing to spend time for the study; approximately one hour for a screening visit and additional 1 hour- for the study assessments. Study assessment will be conducted over 2 visit days, approximately 2 hours per day.
- Either gender
- Any racial or ethnic origin
- SVCM tear lipid thickness  $\leq$  75 nm

Contact lens wearers must refrain from lens wear for two days, including the day of the baseline visit, before the baseline examination and during the entire study.

### Exclusion criteria:

- Use of any ocular prescription medication (such as but not limited to, glaucoma medications, anti-inflammatory eye drops and Restasis) used within 14 days of the screening visit or started prior to the measurement visit(s).
- Currently having punctal plugs inserted in lacrimal puncta
- Current eye disease, infection or inflammation that affects the surface of the eye such as, but not limited to moderate or greater blepharitis and ocular allergy. Clinically significant (active treatment) of blepharitis, Sjogren's disease or other systemic disease that could influence MGD, corneal, conjunctival, or eyelid abnormalities that could influence lipid layer thickness, conjunctivitis of any cause, ocular infection or systemic medication such as diuretics, SSRIs, that could influence tear secretion, or sensitivity to any of the ingredient in the eye drop being tested,
- Past eye surgery, such as, but not limited to, refractive surgery. Subjects who have had cataract removal surgery more than one year ago, but less than 10 years ago may be considered as potential subjects.
- Female subjects may not be pregnant or lactating. (Subject will be asked to self report these conditions.)
- Infectious diseases (for example, hepatitis, tuberculosis) or an immuno-suppressive disease (for example, HIV). (Subjects will be asked to self-report these conditions.)
- Inability to complete the screening and examination

- Inability to provide analyzable data. For example, subjects who cannot keep their eye open during the entire measurement interval (due to early blinking) or provide a readable eye image (due to eyelid laxity) or cannot sit still for 1 minute.

On visit days, to participate in the study, subjects must:

- Refrain from using eye drops/topical medication at least four hours prior to the visit.
- Refrain from eye rubbing prior to and during the assessment and study visit
- Refrain from using eye makeup. If makeup was worn on the screening or measurement day, the subject must remove it at least one hour prior to the study visit appointment.

### Adverse Events

All adverse events will be reported to the IRB and study sponsor, by the PI, within one working day. Adverse Events information will be summarized in the annual report to the IRB as well as to the Sponsor at the end of the study. Adverse events will be assessed and determined by [name] or [name].

### Subject Dismissal

Subjects who, after study team member coaching, are not able to provide analyzable data may be dismissed from the study. Analyzable data is, for example, that which is obtained for the entire measurement interval and provides a readable eye image. Data may not be analyzable if, for example, subjects blink at inappropriate times or have eyelid laxity, to name just two causes issues. These issues are usually revealed at the screening assessment visit. Subjects who cannot provide analyzable data will be dismissed for the study. Subjects who do not keep scheduled visits within the required time frame will be dismissed from the study. Study team members will make reasonable efforts to accommodate subjects' schedules.

### Monitoring Procedures

Although the investigators are trained in Good Clinical Practice, FDA requirements for testing, and protected health information, the sponsor will perform a site visit and monitor data integrity at the study site at the Ohio State University College of Optometry, [name]. A representative of sponsor will conduct study initiation and routine monitoring of the study to assure that the site personnel understands the study enrollment and reporting requirements, and initial review and evaluation of adverse events. The procedures for monitoring may include providing reports from the site that indicate the current enrollment and projected date of study completion and periodic site visits as needed. The frequency and scope of periodic site visits will be based upon enrollment, adverse event reports and overall assessment of site performance.

The center participating in this study shall maintain a set of study files on site. The content of the study files shall include a list of all subjects enrolled, correspondence related to the conduct of the study, the protocol and any amendments, CRF for each subject enrolled in the study, and a log of all those individuals who treat and follow subjects, complete and/or correct CRF, and any other documents required by the sponsor, Federal regulations or IRB requirements.

### Investigator Responsibilities

Clinical investigators are responsible for: 1) ensuring that the study is conducted according to the signed agreement, investigational plan and applicable FDA regulations; 2) protecting the rights, safety, and welfare of subjects under the investigator's care; 3) control of the test article under investigation; 4) ensure that informed consent is obtained.

The Principal Investigator is responsible for the completion, correction and maintenance of patient Case Report Forms, clinical supplies, and other study documents. The investigator must provide adequate time and resources to the study protocol and must be available to the Sponsor and its representatives via telephone, and in person during site visits. The Investigator shall notify the sponsor of any change in the staff assigned to the study project, location of the device or office space utilized, or responsibility to maintain records within 5 working days of the event. Any plans to change the role or responsibility of any clinical investigators associated with the study must be approved by the sponsor, in advance.

The Medical Monitor will review information provided by investigators (or designee) about potential study subjects who otherwise are qualified but fail to meet all eligibility criteria. All protocol deviations require the consent of the Medical Monitor in advance of exposure.

#### Protocol Violations, Discontinuation

In the event that a member of the study team or a representative of sponsor becomes aware of a protocol violation, the investigator and the reviewing IRB shall be informed by written correspondence within one work day. If protocol violations continue, the sponsor may take disciplinary action, including probation and termination of participation in the study. All disciplinary actions will be shared with the reviewing IRB.

#### Discontinuation of the Study

The study may be discontinued due to the loss of instrumentation function (there is only one such instrument) or if patient safety is at risk or data integrity can no longer be assured. The sponsor may discontinue enrollment in the study at any time upon written notification to the clinical investigators. In the event the study is discontinued, sponsor will provide explicit written instruction with regard to study follow-up requirements, maintenance of clinical data, and other pertinent information.
